Title: Written safety planning vs the Safety Net app: A prospective randomized pilot trial
PI: [name], PhD
Site: University of Arkansas for Medical Sciences

once the study is complete. If so, electronic records will be audited to ensure high fidelity with the originals. These electronic copies will also be maintained on secure password-protected UAMS servers. When eventually destroyed, copies will be shredded per UAMS disposal guidelines.

Data collection will be performed through the Research Electronic Data Capture (REDCap) system on a secured UAMS wireless network, and it will be set up in cooperation with the UAMS Translational Research Institute (TRI) in order to assure 21 CFR Part 11 and HIPAA compliance.

Data Analysis

Outcome measures: Number of patients approached who agree to allow trained non-clinical staff to assist them with safety planning (if they do not agree, no other information about the patient will be recorded); the number of patients approached who meet all inclusion/exclusion criteria (if patients are not eligible for the study, no other information about the patient will be recorded); the number of participant safety plans which must be redone either by the peer support specialist, other nonclinical individuals, or clinical staff; the quality of completed safety plans; and patient satisfaction with each method.

Outcome 1: Evaluate the proportion of SI patients approached in the UAMS ED who agree to allow trained non-clinical staff to assist with safety planning. This number is currently unknown.

Outcome 2: Evaluate the proportion of patients approached who meet all inclusion/exclusion criteria. This number may be lower than the number of patients willing to participate in safety planning.

Outcome 3: Evaluate the quality of the completed safety plans. This will be done by retrospective review after the patient has left the ED. The number of safety plans that must be repeated or redone by clinical providers will also be tracked.

Outcome 4: Patient satisfaction with each method. This will be assessed by having the patient rate their experience with the safety planning process on a 7-point Likert scale (*strongly disagree; disagree; moderately disagree; neutral; moderately agree; agree; strongly agree*).

Power calculations and sample size: As this is a pilot study, no formal sample size calculation is planned. The investigators plan a priori to enroll 30 patients. The investigators therefore ask for permission to approach a maximum of 100 patients.

Initially, the randomization scheme will be validated by comparing the groups on key variables that could be associated with outcome (e.g., age, biological sex, prior suicide

Title: Written safety planning vs the Safety Net app: A prospective randomized pilot trial

PI: [name], PhD

Site: University of Arkansas for Medical Sciences

attempts, prior completion of safety plan). Where we identify significant differences between groups, we will either adjust for these variables in analysis or conduct stratified analyses. Categorical variables will be analyzed with chi-square. Continuous variables will be analyzed by ANOVAs. Sub-analyses of potential prognosticators, including biological variables such as sex, will be descriptively presented, as the sample size will not likely permit sufficient testing of these variables.

Ethical Considerations

Written consent will be required for any study procedures. (please see “consent form.”). Please note that all study procedures will be conducted in accordance with all applicable government regulations and University of Arkansas for Medical Sciences research policies and procedures. This protocol and any amendments will be submitted and approved by the UAMS Institutional Review Board (IRB) to conduct the study.

Potential participants will be identified from the ED track board and/or patient triage note. This requires a partial waiver of HIPAA for recruitment purposes only. No PHI will be recorded or disclosed without patient consent. Please see study flow above.

Peers or other research staff will approach the patient in an ED treatment room only if this can be done privately and safely (please see “Training of peers” above). The consent process will also be done privately in the same room. No patients will be approached in the waiting room or in a hall bed. The formal consent of each subject, using the IRB-approved consent form, will be obtained before that subject is submitted to any study procedure. All subjects for this study will be provided a consent form describing this study and providing sufficient information in language suitable for subjects to make an informed decision about their participation in this study. The person obtaining consent will thoroughly explain each element of the document and outline the risks and benefits, alternate treatment(s), and requirements of the study. The consent process will take place as described above, and subjects may take as much time as needed to make a decision about their participation.

Participation privacy will be maintained and questions regarding participation will be answered. No coercion or undue influence will be used in the consent process, including the fact that the PI will not be involved in the recruitment process if he is working in the ED at the time as an attending physician. This consent form must be signed by the subject and the individual obtaining the consent. A copy of the signed consent will be given to the participant, and the informed consent process will be documented in each subject’s research record.

Title: Written safety planning vs the Safety Net app: A prospective randomized pilot trial
PI: [name], PhD
Site: University of Arkansas for Medical Sciences

Dissemination of Data

Results of this study may be used for presentations, posters, or publications. The publications will not contain any identifiable information that could be linked to a participant.

References

1. United States Centers for Disease Control. Web-based injury statistics query and reporting system (WISQARS): Leading causes of death reports, 1981-2016. <https://webappa.cdc.gov/sasweb/ncipc/leadcause.html>. Accessed August 19, 2018.

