Safety planning is a brief, ED-feasible intervention which has been demonstrated to save lives,^{4,5} and has been universally recommended by every recent expert consensus panel on suicide prevention strategies.^{3,6-8} In one popular version of the safety plan developed by Stanley et al,⁴ the patient is encouraged to write out the following items: identifying personal signs of a crisis; helpful internal coping strategies; social contacts or settings which may distract from a crisis; using family members or friends for help when in crisis; mental health professionals who can be contacted when in crisis; and restricting access to lethal means.⁴ In most emergency departments, safety-planning is done by clinical personnel such as psychologists or social workers, but these providers are often too busy to perform safety-planning well or have multiple other patient care responsibilities.

This project aims to answer the following three research questions: (1) Will ED patients with suicidal ideation/attempt accept coaching on safety planning from non-clinical personnel; (2) Are these safety plans of high-enough quality for clinical personnel; and finally, (3) Will ED patients with suicidal ideation/attempt complete safety plans electronically?

Please note that the study will not otherwise alter usual & customary care in the emergency department.

Concerns about peer vulnerability to relapse

[figure not shown]
Anecdotally, there have been concerns that peer-delivered interventions may not be effective in the ED, since peers may be vulnerable to relapse in the stress of the acute-care environment. As some authors have noted, working in acute care is stressful for many individuals, not just peers.⁹ However, it is not true that peers are too “fragile” for a study of this type. Findings from peers in non-ED environments have generally indicated that peers receive positive benefit from the experience,¹⁰ including increased confidence and self-esteem.¹¹ Nonetheless, peers will be given the opportunity to experience the ED environment before committing to this project (please see “Recruitment of peers for this project” and “Training of peers” below). In addition, peers will be closely monitored and debriefed by the sub-investigator of this project ([name]), who is a licensed clinical counselor (please also see “Supervision and debriefing of peers” below). While

Title: Written safety planning vs the Safety Net app: A prospective randomized pilot trial
PI: [name], PhD

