- Prospective participants <18-years or >89-years of age;
- Presently incarcerated or in police custody;
- Non-English speaking;
- Critically-ill;
- Intoxicated with alcohol or other substances;
- ED staff objected against entering room;
- Unwilling or unable to complete the safety plan electronically;
- Unwilling or unable to use a tablet;
- Unwilling or unable to show/email this safety plan to clinical and research staff.

Title: Written safety planning vs the Safety Net app: A prospective randomized pilot trial

PI: [name], PhD

Site: University of Arkansas for Medical Sciences

If participants indicate interest in the study and meet all inclusion/exclusion criteria, informed consent will be obtained using IRB-approved consent forms & processes. If they provide consent, participants (n=30) will be randomized in a 1:1 fashion to either the traditional written safety plan group, in which they will complete a written safety plan with a peer support specialist or other research staff member, or the electronic "Safety Net" safety plan group, in which they will complete an electronic safety plan with a peer support specialist or other research staff member (please see Figure 2 above).

Participants will be randomized using the randomization function in REDCap. All participants will be allowed to complete the safety plan in the privacy of their ED treatment room. Please note that participants will be given a \$25 gift card for participating regardless of which group they are randomized into for the study.

After completing the safety planning process, participants will then be asked to answer a short questionnaire concerning their demographics (e.g., age, biological sex), any history of previous suicidal ideation, suicide attempts, or related behaviors, and satisfaction with the safety planning process.

Regardless of whether the safety plan is completed in the traditional paper format or electronically, this will be shown to the UAMS ED psychiatric registered nurse or social worker for approval and entry into the EMR. Please note that the study will not otherwise modify care in the ED. It is possible, although not likely, that psychiatry consultants could choose to revise, edit, or otherwise start anew with safety planning for a particular patient. If so, the patient will be withdrawn from the study.

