As a licensed clinical counselor, [name] will assess the provider's skill level and will become the role of a teacher, counselor, or consultant based on need. In other words, peers and mental health staffs will be provided with either instruction and direct feedback (i.e., the teacher role), support for reflection and processing of personal experiences (i.e., the counselor role), or encouraging confidence in required skills (i.e., the counselor role) depending on need.

In terms of direct supervision, [name] will be on site during the first week of the intervention to observe performance and operation. She will ensure that the safety plan is being administered, documented, and managed appropriately by each provider (see also "Fidelity of the intervention" below). If deficits are identified, she will work with individuals to make needed improvements. During the first week of intervention implementation, [name] will also conduct an individual face-to-face interview with each peer. Interview questions will be guided by the Consolidated Framework for Implementation Research (CFIR)¹⁹ and focus on identifying and overcoming perceived barriers to implementation of the intervention.

Peers will also be provided with clear instructions on how to obtain help during any difficult or uncomfortable situations during the intervention. After the first week of the intervention, peers may inform ED clinical staff (social worker or psychiatric nurse) on site of such situations so that the staff may continue working on the safety plan with the participant. ED clinical staff are available 24/7 so peers would not have much trouble in finding and asking someone for help with a participant during these situations. Participants who do not complete the safety planning with a peer will be withdrawn from the study, but peers will be informed that their safety and well-being remains a priority when completing the intervention and so they should not hesitate to ask clinical staff for help. Peers may also contact [name] using the contact information provided during

Title: Written safety planning vs the Safety Net app: A prospective randomized pilot trial
PI: [name], PhD
Site: University of Arkansas for Medical Sciences

peer training in order to schedule an in-person meeting. [name] will debrief the peer at these meetings by further discussing the difficult or uncomfortable situations.

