Measurement of safety plan quality: All safety plans will be evaluated by existing ED clinical staff for approval. If it needs to be modified, it will be documented that the research staff had to gather more information from the participant. Safety plans will also later be graded on a numerical rating scale (0-2 or 0-3, depending on grading component) by the investigators using materials developed by Gamarra et al for this purpose.²⁰ Using a “safety checklist,” responses for each of the 6 safety plan steps (with step 3 divided into two parts) and the “most important thing worth living for” section will be rated according to the personalization of the information in each section. In addition, each section will be independently rated for “completeness” (0=not complete, 1=partially complete, 2=complete) and “quality” (0=blank, 1=boilerplate, 2=some evidence of personalization, 3=highly personalized and specific). For instance, in the answer to the question “Warning signs (list 3 items),” patients may simply list “sad” which reflects a low-quality answer. Alternatively, the patient may answer “Feeling like I can’t stop crying or can’t stop being sad” which reflects a higher-quality more personalized answer. Each of the sections in a participant’s safety plan will be graded in this manner, with completeness having a maximum score of 16 and quality having a maximum score of 24. An overall score for the safety plan will be derived by adding the scores for all sections in a participant’s safety plan. Peers and other nonclinical individuals will be trained to coach participants towards higher-quality answers (please see above).

Monitoring: Adverse events or in case of psychiatric emergency

By definition, all patients have presented to the ED for an acute mental health crisis and will be under the care of trained ED physicians, trained ED nurses, trained

Title: Written safety planning vs the Safety Net app: A prospective randomized pilot trial

PI: [name], PhD

Site: University of Arkansas for Medical Sciences

psychiatric ED nurses who typically complete the safety plan, and other psychiatric personnel as appropriate. In the unlikely event of psychiatric decompensation, peers will be instructed to stop the intervention and seek help from qualified personnel in the ED. The intervention will then not be continued.

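### The redo count is defined in two conflicting ways, and neither says whether a plan sent back for more information counts as redone

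*Combined protocol and SAP*

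**What the plan says.** The introduction poses, as its second research question: "Are these safety plans of high-enough quality for clinical personnel".

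The section on measurement of safety plan quality sets up the step at which clinical personnel give that judgement: "All safety plans will be evaluated by existing ED clinical staff for approval". It then describes what follows a plan that falls short: "If it needs to be modified, it will be documented that the research staff had to gather more information from the participant". The same section provides for later grading by the investigators, "with completeness having a maximum score of 16 and quality having a maximum score of 24".

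The Data Analysis section then words the rework count twice. The opening list of outcome measures has "the number of participant safety plans which must be redone either by the peer support specialist, other nonclinical individuals, or clinical staff". The Outcome 3 paragraph, after naming retrospective review of plan quality, adds: "The number of safety plans that must be repeated or redone by clinical providers will also be tracked".

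Two withdrawal rules touch the same event. Under Study Design and Procedures, psychiatry consultants might revise a plan or start again, which the protocol calls unlikely: "If so, the patient will be withdrawn from the study". Under Supervision and debriefing of peers, clinical staff may take over a session that a peer cannot finish: "Participants who do not complete the safety planning with a peer will be withdrawn from the study".

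**The concern.** The two sentences in Data Analysis describe the same kind of event but include different people. Under the list, it does not matter who reworks the plan. Under Outcome 3, the plan enters the count only if a clinical provider reworks it.

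The difference matters because the response that the protocol describes for a plan needing modification is that research staff collect more information. Such a plan was not acceptable to the nurse or social worker as presented, yet on its wording Outcome 3 does not count it. The broader list may not count it either, because nothing says whether a modified or supplemented plan is a redone one.

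At stake is what gets reported for the second research question. The approval step is where clinical personnel say whether a plan coached by nonclinical staff is good enough. A count restricted to clinician repairs reflects partly who did the repair, and not only whether the plan was acceptable.

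**Working it through.** The plan states no redo rate, success threshold or power figure for this count, so there is no such figure to reproduce. The one related figure that can be checked is the grading scale. Six steps with step 3 split in two make 7 sections, and the section on what is worth living for makes 8. Then 8 × 2 = 16 for completeness and 8 × 3 = 24 for quality, as stated.

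**Step 1. Set the definitions side by side.**

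| What happens to the plan | Outcome-measures list | Outcome 3 |
|---|---|---|
| Clinical staff redo it | Counted | Counted |
| Peer or other nonclinical staff redo it | Counted | Not counted |
| Sent back; research staff gather more information | Unclear: is modified the same as redone? | Not counted |
| Psychiatry consultant revises or restarts it; patient withdrawn | Unclear | Unclear |
| Peer cannot finish; clinical staff continue; patient withdrawn | Unclear | Unclear |

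The definitions agree clearly only on the first row.

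**Step 2. Illustrate the size.** From the documents: n = 30, randomised 1:1, so 15 per arm. Assumed, because the documents give neither: k plans not accepted as first presented, and a share s of these repaired by research staff.

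- Broad count = k, provided that modification counts as redoing.
- Narrow count = k × (1 − s).
- Exact (Clopper-Pearson) 95% limits for x of n: lower = the 0.025 quantile of Beta(x, n − x + 1), taken as 0 when x = 0; upper = the 0.975 quantile of Beta(x + 1, n − x).

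For k = 6, the broad count is 6/30 = 20% (7.7% to 38.6%). The narrow count is:

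| s | Narrow count | Rate | 95% interval |
|---|---|---|---|
| 0 | 6 × 1 = 6 | 20.0% | 7.7% to 38.6% |
| 1/3 | 6 × 2/3 = 4 | 13.3% | 3.8% to 30.7% |
| 2/3 | 6 × 1/3 = 2 | 6.7% | 0.8% to 22.1% |
| 1 | 6 × 0 = 0 | 0% | 0% to 11.6% |

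Over the same shares, the narrow count runs from 3 to 0 if k = 3 (broad rate 10%; 2.1% to 26.5%) and from 12 to 0 if k = 12 (broad rate 40%; 22.7% to 59.4%).

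**Step 3. By arm.** With 15 per arm, classifying one plan differently moves an arm's rate by 1/15 = 6.7 percentage points.

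**Step 4. Withdrawals.** If one of six reworked plans belonged to a withdrawn patient who left both numerator and denominator, 6/30 = 20.0% would become 5/29 = 17.2%. The documents do not say whether this would happen.

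**The case against.** The strongest reply is that the broad count is itself a listed outcome measure. Rework by nonclinical staff is therefore within the plan, and nothing says the investigators will ignore it. Outcome 3 says that clinician redos will be tracked as well, which can be read as naming one component of the total. Modifications must be documented, so the event is not lost and the reporting could be settled at analysis. The second research question does not rest on this count alone, because Outcome 3 is first the graded quality of completed plans. Research staff are also not the only route to repair: clinical staff may redo or continue a plan, and consultants may revise one. Finally, calling every supplemented plan a failure would merge adding one missing detail with starting again, which the protocol words differently.

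Much of this stands. It removes any claim that the plan as a whole counts only clinician redos, and it is why the fix separates types of change. It does not remove the inconsistency. Documenting an event does not settle which definition is reported, and the component reading of Outcome 3 is possible but not stated. The grading is only a partial safeguard for this question. The investigators do it, not the approving clinicians; it takes place after the patient has left; no acceptability threshold is given; and the documents do not say whether the first or the modified version is scored.

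**Conclusion.** The point holds as an unresolved inconsistency that should be corrected. Two definitions of the redo count sit in one section, and the treatment of modified plans and of withdrawn patients is unstated. If Outcome 3's wording governs reporting, or modifications are not counted as redone, plans that clinical staff did not accept as first presented could be left out of the count that bears on the second research question.

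The number affected is unknown. The range of 20% down to 0% rests on an assumed 6 of 30 plans not accepted and on a repair share varied from none to all. It shows how far the result could depend on wording and predicts nothing.

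A reader might infer that the count will miss most unaccepted plans and that the research question will get a falsely favourable answer. The documents do not support that. They give no share repaired by research staff, they list the broad count as an outcome, they require modifications to be documented, and they grade quality separately.

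**What to change.** Use one definition in both the outcome-measures list and Outcome 3: a plan counts if the psychiatric nurse or social worker does not approve it as first presented.

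- Report the number and proportion by arm.
- Split it by type of change (supplemented or modified, as against redone), so that a small addition is not read as a restart.
- Split it also by who made the change (research staff or clinical staff).
- Keep in the count any plan that clinical staff or psychiatry consultants revised, continued or restarted, even if the patient is then withdrawn. Show these on their own line, because a consultant may step in after approval and an unfinished plan may never have been presented for it. State that the denominator is all randomised patients.

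The cost is a wording change and one REDCap field recording approval at first presentation, with the type and author of any change as its options. The protocol already requires modifications to be documented, so little extra work falls on staff. The one drawback is that the reported rate may look less favourable.

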Other measures: All participants will complete a brief questionnaire regarding their demographics, history of suicidal behaviors, and satisfaction with the safety planning process. After the visit, the electronic medical record will be searched for the following data: date/time of ED triage and disposition; length of ED stay; ED chief complaint or reason for visit; patient disposition (observation/admission/discharge/transfer); psychiatric diagnoses; and frequency of ED visits 3 months before and after the intervention. Length of ED stay will be compared against two control groups (obtained using AR-CDR): a) length of stay of all ED patients during a similar time period; and b) length of stay of ED patients who presented for SI during a similar time period. No PHI will be recorded for either of these deidentified control groups. Peers and other research staff will also be asked to record the total amount of time that they spent performing the safety plan intervention.

Study retention: The study duration is limited to the ED visit (typically <6 hours for SI patients), with participation in the study limited to the interventions mentioned above. Consequently, no special measures designed to increase retention are planned.

Title: Written safety planning vs the Safety Net app: A prospective randomized pilot trial
PI: [name], PhD
Site: University of Arkansas for Medical Sciences

Recruitment of peers for this project

Peers will be recruited through existing relationships with community suicide prevention organizations (i.e., Arkansas Foundation for Suicide Prevention, Arkansas Governor's Suicide Prevention Council, Veterans Service Organizations, etc.). Eligible recruits will complete an interview with [name] where they will be informed about the responsibilities and expectations of working with this project. Training and supervision of peers and other research staff will be used to further monitor the appropriateness of the individual to assist patients in providing the intervention.

Training of peers and other nonclinical individuals

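### Baseline significance tests decide whether the arm comparison is adjusted or stratified, and the plan score to be compared is not named; both should be fixed before data are seen

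*Combined protocol and SAP*

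**What the plan says.** The analysis paragraph under Power calculations and sample size (Data Analysis) opens: "Initially, the randomization scheme will be validated by comparing the groups on key variables that could be associated with outcome". It gives age, biological sex, prior suicide attempts and prior completion of a safety plan as examples, not as a closed list. The rule follows: "Where we identify significant differences between groups, we will either adjust for these variables in analysis or conduct stratified analyses". Chi-square for categorical and ANOVA for continuous variables come next. No significance level is given. Prognostic sub-analyses are to be descriptive only, "as the sample size will not likely permit sufficient testing of these variables".

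Measurement of safety plan quality defines two section ratings, "with completeness having a maximum score of 16 and quality having a maximum score of 24", and a third score: "An overall score for the safety plan will be derived by adding the scores for all sections". Outcome 3 concerns the quality of completed plans and does not say which score is meant. Outcome 4 is satisfaction: "This will be assessed by having the patient rate their experience with the safety planning process on a 7-point Likert scale". Plans that have to be redone are also counted.

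Study Design and Procedures fixes 30 participants at 1:1. The questionnaire, which covers demographics and "any history of previous suicidal ideation, suicide attempts, or related behaviors", is given after the safety planning process.

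**The concern.** A baseline significance test measures how unequal the arms happen to be. It does not show whether a variable predicts the outcome, which is what decides whether adjustment helps. A strong predictor that is mildly unbalanced is left out, and an irrelevant variable that is badly unbalanced goes in. When something is flagged, the analyst still has to choose between adjusting and stratifying, with the data in hand. Two analysts could then report different estimates from the same 30 patients.

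The same openness affects the outcome itself, because three plan scores could each be presented as the quality result. At stake is whether the reported differences in plan quality, satisfaction and plans redone are reproducible and as precise as the data allow.

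**Working it through.** **Inputs from the documents.** 30 participants at 1:1, so nominally 15 per arm; four named baseline variables; chi-square and ANOVA; the score maxima. The 30 is a chosen pilot number with no effect size, SD or power behind it, so it cannot be re-derived. The maxima can: six steps with step 3 split in two, plus the reason-for-living section, make 8 rated sections; 8 × 2 = 16 and 8 × 3 = 24, as stated. An overall score adding both scales would run to 40.

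**Assumptions.** Two-sided alpha 0.05; independent covariates; sex and prior attempt at 50% prevalence, prior plan at 30%; outcome SD 1; effect 0.8 SD; a range of covariate-outcome correlations. The documents give none of these.

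**How often the rule fires.** Four independent 5% tests: 1 − 0.95⁴ = 0.185. Simulation with plain chi-square gave about 0.18; with continuity correction, about 0.09. A continuous variable is flagged only when the arm means differ by at least t(0.975, 28) × √(2/15) = 0.748 SD.

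**What the rule does to power.** 60,000 simulated trials per setting, 15 per arm, adjusting for every variable with balance p < 0.05:

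| Prognostic variable (correlation) | Rule | Pre-set prior attempt | Unadjusted |
|---|---|---|---|
| None | 54.4% | 54.5% | 56.2% |
| Prior attempt (0.2) | 54.4% | 56.2% | 56.1% |
| Prior attempt (0.3) | 54.8% | 58.6% | 56.3% |
| Prior attempt (0.5) | 54.8% | 66.5% | 55.8% |
| Prior plan instead (0.5) | 55.0% | 54.3% | 55.8% |

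The rule trails the unadjusted analysis by 0.8 to 1.8 points. The pre-set covariate breaks even with unadjusted at a correlation of about 0.2 (R² about 0.04). At 0.5, mean 95% CI widths are 1.51 (rule), 1.31 (pre-set) and 1.48 SD (unadjusted). Pre-setting all four variables when none is prognostic gives 49.7%.

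**Type I error of the rule.** 5.0%, 4.7% and 4.4% at correlations of 0, 0.3 and 0.5. In a separate run, taking the better p-value of adjusting and pooled stratification gave 4.4% to 4.9%.

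**Adjust or stratify.** Suppose a binary variable splits 5/15 v 11/15 (plain chi-square p = 0.028), with within-stratum SD 1. Put v₁ = 1/5 + 1/11 = 0.291 and v₂ = 1/10 + 1/4 = 0.350. The 95% CI half-widths are:

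- pooled strata: t(0.975, 26) × √(1/(1/v₁ + 1/v₂)) = 0.819 SD
- adjusted: 0.818 SD
- strata reported separately: t(0.975, 14) × √v₁ = 1.157 SD and t(0.975, 12) × √v₂ = 1.289 SD

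The choice matters for precision only if strata are reported separately.

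**Choice of score.** Two subscores with error correlation 0.7 (assumed) and a third formed as the sum of their standardised values; the smallest p-value of the three is taken. Type I error is 8.0% to 8.1% unadjusted, and 7.4% to 8.3% when the rule and the adjust-or-stratify choice are added.

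**The case against.** The strongest reply is that the plan does have a default. The chi-square and ANOVA sentences directly follow the rule, so with nothing flagged the comparison is unadjusted. A reader might infer that chance imbalance sets the model throughout; the documents do not support that, since with the four named variables about four trials in five would keep the default, and more with a corrected chi-square. This stands and limits the point to the flagged minority.

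A reader might also infer that any significant difference must be chance, so the comparison could reveal nothing. That holds for everyone randomised. But Study Design and Procedures withdraws participants whose plan psychiatry consultants revise or restart, and Supervision and debriefing of peers withdraws those who do not finish with a peer. If they are left out of the analysis, imbalance among the rest need not be chance. This also stands. It is a reason to show baseline data including those withdrawn, not to let a p-value choose the model. It also makes 15 per arm a nominal figure.

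Third, the harm is small and the trial is a pilot with no stated alpha or power. That sets the priority, but it does not excuse an estimate whose definition depends on the data.

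**Conclusion.** The point holds at modest priority. In about 18% of trials (about 9% with continuity correction) the rule would replace the default model because of imbalance rather than prognostic value. In the settings simulated it cost about 1 to 2 power points against a fixed unadjusted analysis. Its shortfall against a pre-set covariate is large only if that covariate is prognostic: about 55% v 67% at an assumed correlation of 0.5 and effect of 0.8 SD. All of this rests on assumed alpha, prevalences, independence and effect size, with a continuous outcome; the 7-point satisfaction rating was not simulated.

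A reader might infer that testing and then adjusting produces false positives. It does not: the rule's type I error is at or slightly below 5%. Inflation, to about 7-8%, comes from the separate open choice among three plan scores. Outcomes 1 and 2 are proportions of patients approached, before randomisation, and are unaffected. Outcome 3 does not say outright that quality is compared by arm; that follows from the trial's stated comparison of electronic with written plans and from the adjustment rule itself.

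**What to change.** Replace the test-then-adjust rule with a descriptive baseline table by arm, including withdrawn participants where data exist. Before data are seen, name one plan score, saying whether the overall score adds both scales, and one fixed between-arm comparison each for that score, for satisfaction (saying whether the rating is treated as continuous or categorical) and for the number of plans redone.

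Each comparison is either unadjusted or has one named covariate used whatever the balance. The covariate should be a fact the intervention cannot change, such as age, or suicide history if it is asked before the intervention; at present it is self-reported afterwards. Prior completion of a safety plan is not named among the items collected ("All participants will complete a brief questionnaire regarding their demographics, history of suicidal behaviors, and satisfaction with the safety planning process"), so it would have to be added before it could be used. Do not fix all four variables at this sample size. Report each difference with a 95% CI and label any other adjustment a sensitivity analysis.

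The cost is a few sentences in an IRB amendment. Using a covariate also costs one degree of freedom and about 1.5 to 2 power points against unadjusted if it is not prognostic. If no covariate can be defended in advance, the fixed unadjusted comparison is sound.
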